1.2.1. Rationale for the study design

A recent CHMI study (MALARIA-071) ***demonstrated superior protection against malaria infection*** associated with the use of a fractional third dose in a 0, 1, 7-month schedule with a vaccine efficacy against infection of 86.7% (95% CI: 66.8; 94.6; p<0.0001) versus 62.5% (95% CI: 29.4; 80.1; p=0.0009) in the standard 0, 1, 2-month schedule. The incremental efficacy of the 0, 1, 7-month schedule over the 0, 1, 2-month schedule was 64.4% (95% CI: -7.9; 88.3; p=0.0741) [Regules, 2016]. The current study intends to establish POC for a fractional dose schedule under conditions of natural exposure. The study will be conducted in children 5-17 months old at first vaccination living in areas of mid to high malaria transmission, in line with the age group recommended by the World Health Organization (WHO) [WHO, 2016]. Infants 6-12 weeks old will not be included in this POC study to avoid interference of co-administration with the standard Expanded Program on Immunization (EPI) vaccines.

Results from this study will be critical in informing future possibilities for the development of vaccine-based strategies which, in combination with other interventions, may contribute to the malaria elimination agenda.

The study proposed herein will include five study groups. One group (R012-20) will receive the standard schedule consisting of RTS,S/AS01_E full dose given at Month 0, Month 1, Month 2 and a fourth dose at Month 20. This corresponds to the schedule that received a positive scientific opinion from EMA. The four other groups will receive alternative schedules as follow:

- Group R012-14-mD will receive RTS,S/AS01_E full dose at Month 0, Month 1, Month 2, an early fourth dose at Month 14 and yearly full doses at Month 26 and Month 38.
- Group Fx012-14-mFxD will receive RTS,S/AS01_E full dose at Month 0 and Month 1, RTS,S/AS01_E fractional dose (1/5th dose) at Month 2 and yearly fractional doses at Month 14, Month 26, Month 38.
- Group Fx017-mFxD will receive RTS,S/AS01_E full dose at Month 0 and Month 1, RTS,S/AS01_E delayed fractional third dose (1/5th dose) at Month 7 and yearly fractional doses at Month 20 and Month 32.
- Control group: will receive three doses of rabies vaccine at Month 0, Month 1 and Month 2.

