9.2. Detecting and recording adverse events and serious adverse events

9.2.1. Time period for detecting and recording adverse events and serious adverse events

All AEs starting within 30 days following administration of each dose of study vaccines (Day 0 to Day 29) must be recorded into the appropriate section of the eCRF, irrespective of intensity or whether or not they are considered vaccination-related.

The time period for collecting and recording SAEs will begin at the first receipt of study vaccine (Day 0) and will end at the last study visit (Month 50) for each subject. See Section [9.3](#) for instructions on reporting of SAEs.

All AEs/SAEs leading to withdrawal from the study will be collected and recorded from the time of the first receipt of study vaccine (Day 0) until study end (Month 50).

In addition to the above-mentioned reporting requirements and in order to fulfil international reporting obligations, SAEs that are related to study participation (i.e. protocol-mandated procedures, invasive tests, a change from existing therapy) or are related to a concurrent GSK medication/vaccine will be collected and recorded from the time the subject consents to participate in the study until she/he is discharged from the study.

The time period for collecting and recording of AEs of specific interest will begin at the first receipt of study vaccine (Day 0) and will end at the last study visit (Month 50) See section [9.3](#) for instructions on reporting of AEs of specific interest.

Solicited local and general AEs will be collected in the first 50 subjects enrolled in each group (reactogenicity sub-cohort) during four days (day of vaccination and three subsequent days) after Dose 3 of study vaccine (all groups including controls), after Dose 4 (R012-20, R012-14-mD, Fx012-14-mFxD and Fx017-mFxD), after Dose 5 (R012-14-mD, Fx012-14-mFxD and Fx017-mFxD) and after Dose 6 (R012-14-mD and Fx012-14-mFxD). On the day of vaccination the evaluation will be carried out by the study physician at the study center. On Days 1, 2 and 3 after vaccination, trained study personnel will visit the children to record solicited AEs on diary cards.

An overview of the protocol-required reporting periods for AEs and SAEs is given in [Table 27](#).

Table 27 Reporting periods for collecting safety information

Study visits	1	2			3			4			10			18			24			27			30			33			38
Event	Scr*	Vac 1			Vac 2			Vac 3			Vac 4			Vac 5			Vac 6			Vac 7			Vac 8			Vac 9			Study end

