10.2.2. Subject withdrawal from investigational vaccines

A 'withdrawal' from the investigational vaccines refers to any subject who does not receive the complete treatment, i.e. when no further planned dose is administered from the date of withdrawal. A subject withdrawn from the investigational vaccines may not necessarily be withdrawn from the study as further study procedures or follow-up may be performed (safety or immunogenicity) if planned in the study protocol.

Information relative to premature discontinuation of the investigational vaccines will be documented on the vaccine administration screen of the eCRF. The investigator will document whether the decision to discontinue further vaccination/treatment was made by the subject's parent(s)/LAR(s) or by the investigator, as well as which of the following possible reasons was responsible for withdrawal:

- Serious adverse event.
- Non-serious adverse event.
- Other (specify).

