11.2. Secondary endpoints

- **Efficacy:**
 - The occurrence of clinical malaria meeting the primary and secondary case definitions from Day 0 up to Month 50.
 - The occurrence of incident *P. falciparum* infections from Day 0 to Month 50.
 - The prevalence of *P. falciparum* infections defined by positive blood slide at each cross-sectional survey.
- **Immunogenicity: Immune response to the CS and HBs antigens (immunogenicity subset)**
 - *Anti-CS antibody concentrations and seropositivity measured before Dose 1, one month post-Dose 2 (group Fx017-mFxD only), before and one month post-Dose 3, before and one month after Dose 4, before and one month after each yearly dose and at study end (Month 50).*
 - Anti-HBs antibody concentrations and seropositivity measured before Dose 1, one month post-Dose 2 (group Fx017-mFxD only), before and one month post-Dose 3, before and one month after Dose 4, before and one month after each yearly dose and at study end (Month 50).

Amended 14 November 2019

- **Safety**
 - The occurrence of SAEs (all, fatal and related) during the whole study period according to the MedDRA classification.
 - The occurrence of AEs and SAEs leading to withdrawal from further vaccination from Dose 1 (Day 0) up to Month 50, according to the MedDRA classification.
 - The occurrence of severe malaria cases and cerebral malaria cases during the whole study period.
 - The occurrence of pIMDs from Day 0 up to Month 50, according to the MedDRA classification.
 - The occurrence of meningitis from Day 0 up to Month 50, according to the MedDRA classification.
 - The occurrence of seizures within 30 days (day of vaccination and 29 subsequent days) after each dose of study vaccine, according to the MedDRA classification.
 - The occurrence of generalized convulsive seizure within seven days (day of vaccination and six subsequent days) after each dose of study vaccine, according to the Brighton collaboration guidelines [[Bonhoeffer](#), 2004].

- The occurrence of unsolicited AEs within 30 days (day of vaccination and 29 subsequent days) after each dose of study vaccine, according to the MedDRA classification.
- The concentration of biochemistry (ALT, creatinine) and hematology (hemoglobin, WBC, platelets) parameters in the first 50 subjects (25 subjects per site) enrolled in each group (reactogenicity sub-cohort) before Dose 3, seven days post-Dose 3 and 30 days post-Dose 3.
- **Reactogenicity (reactogenicity sub-cohort)**

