The percentage of subjects reporting an SAE (all, fatal, related) from Dose 1 (Day 0) until Month 14, from Day 0 until Month 21, from Day 0 until Month 26, from Day 0 until Month 33 and over the whole study duration (Dose 1 [Day 0] until Month 50), classified by the MedDRA preferred term level, will be tabulated with exact 95% CI.

The percentage of subjects reporting an AE or SAE leading to withdrawal from further vaccination from Dose 1 (Day 0) until Month 50, classified by the MedDRA preferred term level, will be tabulated with exact 95% CI.

The percentage of subjects reporting severe malaria cases and cerebral malaria cases from Day 0 up to Month 14, Day 0 up to Month 21, Day 0 up to Month 26, Day 0 up to Month 33 and Day 0 up to Month 50 and over successive years within the study will be tabulated with exact 95% CI.

The percentage of subjects reporting pIMDs from Day 0 up to Month 14, Day 0 up to Month 21, Day 0 up to Month 26, Day 0 up to Month 33 and Day 0 up to Month 50, classified by the MedDRA preferred term level will be tabulated with exact 95% CI.

The percentage of subjects reporting meningitis from Day 0 up to Month 14, Day 0 up to Month 20, Day 0 up to Month 26, Day 0 up to Month 32 and Day 0 up to Month 50 classified by the MedDRA preferred term level will be tabulated with exact 95% CI.

The percentage of subjects reporting seizures occurring within 30 days (day of vaccination and 29 subsequent days) after each dose of study vaccine, classified by the MedDRA preferred term level will be tabulated with exact 95% CI.

For generalized convulsive seizures occurring within seven days following a dose of study vaccine, an analysis will be performed based on the Brighton Collaboration guidelines [Bonhoeffer, 2004]. This includes descriptive tables of the time relationship of seizures to vaccination, the duration of seizures and the level of diagnostic certainty.

Biochemistry (ALT, creatinine) and hematology (hemoglobin, WBC, platelets) values that are outside of the reference ranges (see protocol section 7.5.2.1) will be described for the reactogenicity sub-cohort (first 50 subjects enrolled in each group) before Dose 3, seven days post-Dose 3 and 30 days post-Dose 3. Frequency distribution of results by toxicity grades will be tabulated by group.

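### The 50-month percentage for AEs stopping further vaccination mixes tolerability with the number of doses scheduled; a by-dose-due table would separate the two at little cost

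*SAP*

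**What the plan says.** Group labels below are those of the SAP.

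Protocol 11.2 lists as a secondary safety endpoint "The occurrence of AEs and SAEs leading to withdrawal from further vaccination from Dose 1 (Day 0) up to Month 50". Protocol 11.10 and SAP 7.5.1 analyse it in almost identical words: "The percentage of subjects reporting an AE or SAE leading to withdrawal from further vaccination from Dose 1 (Day 0) until Month 50", by MedDRA preferred term with an exact 95% CI. The safety analysis is on the Exposed Set, meaning every child with at least one dose. This endpoint has only the 50-month window. In the same section, SAEs, pIMDs and meningitis each have several shorter windows as well, and SAEs and unsolicited AEs are also tabulated after each dose.

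Protocol 10.2.2 says that a child is withdrawn from vaccine when the complete treatment is not received, that is, "when no further planned dose is administered from the date of withdrawal".

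The schedules in protocol 1.2.1 end at different times. Control children "will receive three doses of rabies vaccine at Month 0, Month 1 and Month 2". R012-20 has a "full dose given at Month 0, Month 1, Month 2 and a fourth dose at Month 20". R012-14 has "an early fourth dose at Month 14 and yearly full doses at Month 26 and Month 38", and Fx012-14 follows the same calendar with fractional doses from Month 2. Fx017-20 has doses at Months 0, 1, 7, 20 and 32.

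Protocol 9.2.1 words the collected item differently: "All AEs/SAEs leading to withdrawal from the study will be collected and recorded from the time of the first receipt of study vaccine". Table 27, in that same section, refers to further vaccination, as do the endpoint and the analysis.

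**The concern.** A child who has had every planned dose has nothing left to be withdrawn from. A Control child with a serious event at Month 10 cannot score, whereas a child in any RTS,S group with the same event at Month 10 can, because each of those groups still has a dose due. A single percentage over Day 0 to Month 50 gives both children the same place in the denominator. The group figures then reflect how many doses were scheduled as well as how well they were tolerated.

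This bears on a question the study was set up to answer. Protocol 1.2 records a regulator's request for data on the safety of multiple yearly doses. Someone reading across the columns could take a difference in scheduled doses for a difference in tolerability. That applies to the RTS,S groups against Control, and also to R012-20 against R012-14.

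**Working it through.** The documents give no expected rate, power or precision for this endpoint, so there is no planned figure to reproduce. The check is what the table would show on average if tolerability were identical in all groups.

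**Inputs.** Dose calendars are from protocol 1.2.1. Group size is about 300 (protocol 6.2.2.2.1). The period at risk runs from Day 0 to the last planned dose.

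| Group | Last planned dose | Share of 50 months | Doses after dose 1 (k) |
|---|---|---|---|
| Control | Month 2 | 4% | 2 |
| R012-20 | Month 20 | 40% | 3 |
| Fx017-20 | Month 32 | 64% | 4 |
| R012-14, Fx012-14 | Month 38 | 76% | 5 |

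**Model A: equal risk q per dose due (q assumed).** The expected percentage is 1 − (1 − q)^k. At q = 0.5%:

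- Control: 1 − 0.995² = 1.00%, or 2.99 of 300
- R012-20: 1 − 0.995³ = 1.49%, or 4.48
- Fx017-20: 1 − 0.995⁴ = 1.99%, or 5.96
- Month-38 groups: 1 − 0.995⁵ = 2.48%, or 7.43

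The ratio of the Month-38 groups to Control is 2.48. It stays between 2.46 and 2.50 for q from 0.05% to 1%.

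**Model B: constant rate h per year while a dose is due (h assumed).** The expected percentage is 1 − exp(−h·t/12), with t the months at risk. At h = 0.5% per year the results are Control 0.08%, R012-20 0.83%, Fx017-20 1.32% and Month-38 groups 1.57%. The last is 18.9 times Control, and the ratio is 18.4 to 19.0 for h from 0.1% to 2%. This is close to the ratio of times at risk, 38/2 = 19.

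The models answer for different mechanisms: A for reactions tied to a dose, B for background illness that happens to stop vaccination. The documents do not say which dominates.

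**How often the observed table would show an excess.** With 300 per group and exact binomial probabilities:

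| Comparison with Control | Model A, q = 0.05% to 1% | Model B, h = 0.1% to 2% |
|---|---|---|
| Month-38 group higher | 0.43 to 0.97 | 0.60 to more than 0.999 |
| R012-20 higher | 0.29 to 0.74 | 0.38 to 0.998 |

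At q = 0.05%, a Month-38 group ties with Control with probability 0.43 and falls below it with probability 0.14.

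**Does a denominator tied to doses due remove the effect?** Under Model A, each dose-due percentage is q in every group, by construction. Under Model B, events per person-year while a dose is due are equal. At h = 0.5% they are 0.25/50.0, 2.49/497.9, 3.97/794.7 and 4.71/942.5 for Control, R012-20, Fx017-20 and each Month-38 group, all 0.005.

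One limit applies to by-dose comparisons. Protocol Table 14 allows 21–35 days from dose 2 to dose 3 in the 0,1,2-month groups, but 161–203 days in Fx017-20. Under Model B at h = 0.5%, one month before dose 3 gives 1 − exp(−0.005/12) = 0.042%, and six months gives 1 − exp(−0.0025) = 0.250%. That is a six-fold difference from the interval alone. The intervals before dose 4 also differ: 336–392 days in R012-14 and Fx012-14, 518–574 in R012-20 and 364–420 in Fx017-20. Like-for-like comparisons therefore exist at dose 2 for all groups, at dose 3 for the 0,1,2-month groups, and at every dose for R012-14 against Fx012-14.

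**The case against.** The strongest reply is that the objective is safety for each schedule. A higher cumulative percentage under a six-dose schedule is then a real property of that schedule. This stands, and it is a reason to keep the cumulative table. It does not supply a per-dose reading, and the plan offers none for this endpoint.

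Second, nothing formal depends on the table. It gives within-group percentages with exact CIs, and SAP 8 says secondary endpoints outside the hierarchical test are descriptive. This stands too. A reader might infer that a planned comparison is biased, but no difference, ratio or test against Control is planned here.

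Third, a reader might infer that the design guarantees a visible vaccine excess. It does not. It raises the expected percentage, and with few events the observed figures can tie or reverse.

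Fourth, a reader might infer from protocol 9.2.1 that AE-related withdrawal from the study is collected and then left unanalysed. SAP 7.1.2 tabulates withdrawn children by reason, and the reasons in protocol 10.2.1 include serious and non-serious AEs. Nor is 9.2.1 a rival endpoint: it is one sentence out of line with Table 27, the endpoint and both analysis sections.

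Finally, other safety outcomes are reported on equal terms. SAEs, severe malaria, pIMDs and meningitis are tabulated to Month 50 in all groups, and SAP 7.2 tabulates doses received by group. This limits the harm but leaves this endpoint unlabelled.

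**Conclusion.** The point holds as a cheap improvement. The event can be scored only while a planned dose is due, the last dose ranges from Month 2 to Month 38, and neither document gives an at-risk denominator, a common window or a caveat. At equal tolerability, every RTS,S group has a higher expected percentage than Control. For the Month-38 groups the ratio is about 2.5 if risk is equal per dose due and about 19 if the rate is constant over time. Not all yearly-dose groups run to Month 38: Fx017-20 ends at Month 32.

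The direction follows from the schedule and the protocol 10.2.2 definition. The sizes rest on assumed rates, on 300 children per group and on equal follow-up. If the wording of 9.2.1 were the intended one, events could occur to Month 50 in every group, which is why the two must be reconciled.

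**What to change.** In SAP 7.5.1:

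- Keep the cumulative Day 0 to Month 50 percentage as a description of each schedule, labelled with each group's at-risk period (to Month 2, 20, 32 or 38).
- Add a table by dose due, doses 2 to 6, with children still scheduled for that dose as denominator.
- Compare with Control only at dose 2 (all groups) and dose 3 (0,1,2-month groups). Show Fx017-20 dose 3 separately because of its longer interval. Compare R012-14 with Fx012-14 at every dose.
- For a measure that all groups can score to Month 50, cross-refer to the withdrawals by reason in SAP 7.1.2.

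In protocol 9.2.1, reconcile the sentence on withdrawal from the study with Table 27 and the endpoint.

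Reasons for stopping vaccine and for leaving the study are already recorded separately (protocol 10.2.1 and 10.2.2), so no new data are needed. The cost is some SAP wording, one protocol clarification and one more small descriptive table.

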Important potential risk: Delayed increased incidence of severe malaria in relation with delayed acquisition of blood-stage immunity	In the large phase III study MALARIA-055 PRI, an increased incidence of severe malaria relative to the control group has been observed, starting around two years after RTS,S/AS01 _E primary vaccination course, in children 5-17 months of age at first dose that did not receive a RTS,S/AS01 _E fourth dose. This higher risk of severe malaria might result from a delay in the acquisition of blood-stage immunity associated with a decreased exposure in children vaccinated with RTS,S/AS01 _E relative to controls.	All studies with long term follow-up showed that the overall benefit stays in favor of the vaccine despite delayed acquisition of blood-stage immunity. The receipt of a fourth dose increased that benefit. The study MALARIA-055 PRI showed no evidence of a delayed increased incidence in severe malaria in children who received a fourth dose, up to two years post-fourth dose. In the present study all RTS,S/AS01 _E groups will receive at least one additional dose (fourth dose). Severe malaria cases will be reported as serious adverse events (SAEs). The occurrence of severe malaria cases will be described.
Important potential risk: Hypersensitivity (including anaphylaxis)	As with other vaccines, hypersensitivity and anaphylaxis to one or several components of the vaccine can rarely occur. One case of erythema multiforme and two cases of bronchospasm within 30 days following RTS,S/AS01 _E vaccination were reported as hypersensitivity reactions in past studies. No case of anaphylaxis has been reported following RTS,S/AS01 _E vaccination to date.	Subjects will be observed closely for at least 30 minutes following administration of the vaccine with appropriate medical treatment readily available in case of anaphylaxis. History of anaphylaxis post-vaccination and history of any reaction or hypersensitivity likely to be exacerbated by any component of the vaccine are exclusion criteria in this study (see Section 5.3). Previous anaphylactic reaction to a vaccine is a contraindication to further experimental vaccinations in this study (see Section 7.5).

Important potential/identified risk	Data/rationale for risk	Mitigation strategy

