7.5. Analysis of safety and reactogenicity

7.5.1. Analysis of safety and reactogenicity planned in the protocol

The primary analysis of safety will be based on the ES. Analyses containing only solicited data will be based on the solicited safety set.

Among the reactogenicity sub-cohort (first 50 subjects enrolled in each group) the percentage of subjects with at least one local AE (solicited and unsolicited), with at least one general AE (solicited and unsolicited) and with any AE during the solicited follow-up period (i.e. four days post-Dose 3, Dose 4, Dose 5 and Dose 6) will be tabulated with exact 95% CI after each vaccine dose and overall. The percentage of doses followed by at least one local AE (solicited and unsolicited), by at least one general AE (solicited and unsolicited) and by any AE will be tabulated for the whole solicited follow-up period (i.e. four days post-Dose 3, Dose 4, Dose 5 and Dose 6), with exact 95% CI. Similar tables will be generated for Grade 3 AEs and AEs considered as causally related to vaccination.

Among the reactogenicity sub-cohort (first 50 subjects enrolled in each group), the percentage of subjects reporting each individual solicited local and general AE during the solicited follow-up period (i.e. four days post-Dose 3, Dose 4, Dose 5 and Dose 6) will be tabulated with exact 95% CI. The percentage of doses followed by each individual solicited local and general AE will be tabulated for each dose and for the whole solicited follow-up period (i.e. four days post-Dose 3, Dose 4, Dose 5 and Dose 6), with exact 95% CI. Similar tables will be generated for Grade 3 AEs, causal events and for fever, temperature in 0.5°C increments.

The verbatim reports of unsolicited symptoms will be reviewed by a physician and the signs and symptoms will be coded according to the MedDRA. The percentage of subjects with at least one report of an unsolicited AE classified by the MedDRA preferred term level, occurring within 30 days (day of vaccination and 29 subsequent days) after each dose of study vaccine will be tabulated with exact 95% CI.

204889 (Malaria-094) Statistical Analysis Plan

The percentage of subjects reporting an SAE (all, fatal, related) occurring within 30 days (day of vaccination and 29 subsequent days) after each dose of study vaccine, classified by the MedDRA preferred term level will be tabulated with exact 95% CI.

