7.5.2.3. Additional analysis for severe malaria

A listing for severe malaria cases with associated sign and symptoms will be provided. The same listing will be provided for cerebral malaria cases.

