11.1.4. Statistical methodology

11.1.4.1. Exact confidence intervals around proportions

The exact CIs around within-group proportions are derived using the method of Clopper and Pearson [Bonhoeffer, 2004; Clopper, 1934].

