11.1.4.2. Standardized asymptotic confidence intervals around differences in proportions

The standardized asymptotic CIs around differences in proportions are derived using the method of Mietinnen and Nurminen [Miettinen, 1985].

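### Severe malaria, a risk the protocol defines relative to Control, is tabulated only within each group; adding an estimated contrast with Control would be a cheap improvement

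*SAP*

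**What the plan says.** Protocol 1.3.1, Table 1, lists a delayed rise in severe malaria as an important potential risk. Its basis is that in the Phase III trial "an increased incidence of severe malaria relative to the control group has been observed, starting around two years after" the primary course. The same row adds three limits: that excess was in children who had no fourth dose; none was seen up to two years after a fourth dose; and every RTS,S group here is due at least one. The analysis promised is "The occurrence of severe malaria cases will be described".

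SAP 7.5.1 gives the percentage of subjects with severe and cerebral malaria from Day 0 to Months 14, 21, 26, 33 and 50 "and over successive years within the study will be tabulated with exact 95% CI". Protocol 11.10 plans the same with three cumulative windows (Months 14, 26 and 50). SAP 11.1.4.1 defines the interval: "The exact CIs around within-group proportions are derived using the method of Clopper and Pearson". SAP 7.5.2.3 adds "A listing for severe malaria cases with associated sign and symptoms will be provided", and the same for cerebral malaria. SAP 11.1.4.2 does contain a between-group method, "The standardized asymptotic CIs around differences in proportions are derived using the method of Mietinnen and Nurminen", but as annex text that no safety output calls on. SAP section 8 sets no safety contrast.

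**The concern.** The risk is comparative: it is an excess over Control that appears late. The planned output is five separate percentages, each with its own interval. Nothing in the plan turns them into a difference or ratio with a confidence interval, for one arm or for all RTS,S arms together. Percentages of subjects also ignore unequal follow-up, which matters most in the later years, when this risk would appear.

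At stake is how clearly an imbalance is reported. After the interim analyses the IDMC may recommend suspending further vaccinations or ending groups (SAP 9.1), and the Day 0 to Month 33 table covers the second interim. Readers of the final report face the same question. Both would have to work out the excess and its uncertainty themselves.

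**Working it through.** **Plan's own figure.** There is none to reproduce. The documents state no severe malaria rate, precision or power; the power in protocol 11.4 is for the primary efficacy endpoint.

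**Inputs.** About 300 per group, with four RTS,S groups and one Control (protocol 6.2.2.2.1). Assumed: 280 per arm contributing in a given year, so 4 × 280 = 1120 pooled; yearly Control risk p0 of 0.5% to 5%, with 1% to 2% as the central range; a true excess of twofold or threefold.

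**One worked table.** Suppose 16/300 (5.33%) in an RTS,S arm and 6/300 (2.00%) in Control in one year.
- Separate exact 95% CIs: 3.08% to 8.52% and 0.74% to 4.30%. They overlap.
- Pooled score statistic, with p = 22/600 = 0.03667: z = 0.03333 / √(0.03667 × 0.96333 × 2/300) = 0.03333 / 0.01535 = 2.17.
- Miettinen-Nurminen difference: 3.3 points, 95% CI 0.35 to 6.72.
- Rate ratio, if person-time is equal: 16/6 = 2.67; SE of the log = √(1/16 + 1/6) = 0.479; 95% CI exp(0.981 ± 0.938) = 1.04 to 6.8.
- With 6/300 in Control, the score CI excludes zero from 15/300, but the separate intervals stop overlapping only from 21/300 (7.0%).

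**Detection probabilities.** Exact enumeration: the sum over x0 and x1 of Bin(x0; n0, p0) × Bin(x1; n1, p1) × I(rule met). The score rule is z > 1.96. The overlap rule is that the lower Clopper-Pearson limit in RTS,S exceeds the upper limit in Control.

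| Control risk | True excess | One arm (280 v 280): score / overlap | Pooled (1120 v 280): score / overlap |
|---|---|---|---|
| 0.5% | ×2 | 8% / 0.1% | 3% / <0.1% |
| 0.5% | ×3 | 20% / 0.8% | 17% / 1.4% |
| 1% | ×2 | 15% / 1% | 14% / 3% |
| 1% | ×3 | 40% / 8% | 48% / 19% |
| 2% | ×2 | 28% / 5% | 35% / 13% |
| 2% | ×3 | 70% / 30% | 85% / 60% |
| 5% | ×2 | 62% / 25% | 79% / 53% |
| 5% | ×3 | 98% / 88% | >99% / 99% |

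At 0.5%, pooling does not help: Control is expected to have only 280 × 0.005 = 1.4 cases a year, and that count limits any contrast.

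**Cost in false alarms.** With both groups at 2%, one score contrast is outside ±1.96 in 4.8% of trials, against 0.2% to 0.4% for non-overlap. Four arms plus the pooled contrast over four study years make 20 contrasts sharing one Control. In simulation with no true effect at 1% to 2% risk, at least one falls outside ±1.96 in about 49% of trials, and at least one in the harm direction in about a quarter.

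**The case against.** The case for leaving the plan alone has substance. The safety objective is worded per schedule, and the protocol promises description only, so per-group tables match the stated design. The yearly split addresses lateness, Control is tabulated beside the other groups, every case is reported as an SAE and listed, and an IDMC oversees the trial. No passage tells anyone to judge by whether intervals overlap; that is a presumed reader habit, and a difference can be computed by hand from the tabulated counts. The direct contrast is itself weak for modest excesses. The annex method is a sponsor standard rule, so its not being assigned is no proof of an oversight, and table shells sit in a file outside these documents.

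Most of this stands, and it limits the point to a reporting improvement. It does not supply the missing estimate. The reassurance about a fourth dose is also narrower than it looks. It reaches two years after that dose, which in the Phase III trial came 18 months after the third. R012-20 has that spacing, but its follow-up runs to Month 50, 30 months after its Month 20 dose. The other three arms have the fourth dose 12 or 13 months after the third, and two of them use a fractional one.

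Two stronger readings are tempting. A reader might infer that a late excess would go unnoticed; the yearly tables that include Control contradict that. A reader might also want a Control column in the 30-day post-dose SAE tables for doses that Control does not receive. The documents do not support that either. Vaccination is deferred for fever or acute illness (protocol 6.6.14 and 7.5), whereas a Control window starting at a routine visit has no such filter. At Months 7, 14, 26, 32 and 38 Control has only field-worker visits (protocol Tables 11 to 13), while the arms being vaccinated have clinic visits with SAE recording. The comparison would carry selection and ascertainment bias. For the same reason a split by time since last dose is not useful, since it has no natural meaning for Control after Month 2.

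**Conclusion.** The point holds as a cheap improvement. For a risk that the protocol itself frames against Control, the plan shows the group percentages by year but never estimates the excess or its uncertainty. At an assumed yearly Control risk of 1% to 2% with 280 per arm, a direct contrast detects a threefold excess in about 40% to 70% of trials and a doubling in about 15% to 28%. Comparing separate exact intervals would give about 8% to 30% and 1% to 5%. The gap depends on the assumed rates and on readers using overlap as a guide. Below about 1% Control risk, neither approach is informative about a doubling, so the added contrast should be read as estimation and not as a test that could rule the risk out.

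**What to change.** In SAP 7.5.1, for severe malaria (and cerebral malaria if counts allow), add the incidence rate difference and rate ratio versus Control with 95% CIs. Use person-time, adapting the time-at-risk convention of SAP 7.3.2.1, or use the Miettinen-Nurminen difference of SAP 11.1.4.2 if percentages are kept. Report by study year and over Day 0 to Month 50. Name all RTS,S arms pooled versus Control as the lead contrast, followed by each arm. Label the set as descriptive and unadjusted for multiplicity, in line with the descriptive stance of SAP section 8 on other secondary endpoints. Leave the 30-day post-dose SAE tables as planned.

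The cost is a few extra table columns from data already collected. The downside is a set of low-powered contrasts sharing one Control group, in which an isolated interval excluding no difference is to be expected by chance; the text beside the table should say so.
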